Maintenance Transcranial Magnetic Stimulation in Major Depressive Disorder

NCT04076644

12/17/2019

BIOMEDICAL RESEARCH PROTOCOL

UNIVERSITY OF MISSOURI

Project Title: Maintenance of response to Transcranial Magnetic Stimulation (TMS) in Major Depressive Disorder (MDD) using monthly TMS treatment

IRB Number: 2013884

Version Number: 3

Version Date: 12/17/2019

Principal Investigator: [name]

Funding Source:

Clinical Trial Phase: *IV*

Clinicaltrials.gov Number:

Study Drug/Study Device: *Magventure/Magvita TMS machine*

I. Research Objectives/Background

Transcranial Magnetic Stimulation (TMS) has been established as an effective and safe method to treat Major Depressive Disorder (MDD). Large randomized sham controlled trials (1,4), and over a decade of clinical use since it was FDA approved for acute treatment of MDD in 2008, has shown TMS to be a promising treatment after medications and psychotherapy have failed to alleviate depressive symptoms. TMS is non-invasive, and uses a small but powerful pulsed magnetic field placed over the dorsolateral-prefrontal-cortex (DLPFC), a part of the brain thought to be associated with depression. In general, treatments are given 5 times for week for 4-6 weeks. This treatment protocol results in an effectiveness of roughly 2/3 of patients seeing a clinically significant benefit, while 1/3 of those patients experience a complete remission of their depressive symptoms (2). TMS is also a relatively safe treatment and has very little if any side effects, the most common being a slight headache after the treatment (5,6).

Given that treatment resistant MDD is a chronic disease with no known cure, management of symptoms mostly consists of trialing and failing medications whose positive effects on symptomology are of limited time course. TMS is no different. Patients that respond or remit after a TMS course will most likely see a relapse in their depressive symptoms at some point after their acute TMS treatment course is completed (3,7,8). The time course of response or remission after acute TMS treatment varies between individuals from weeks to years, and there is no way to predict the length of positive outcomes. Research has shown that close to 40% of patients will see symptom worsening, and another 10% will have a relapse within 6 months post-acute treatment course (3). Interestingly, data and clinical evidence has shown that if a patient responds to TMS and relapses back into a depressive episode, a new TMS treatment course will provide the same benefits as the original TMS course (3). In other words, if TMS works for the patient, it will most likely work again. Given the relative safety and the fact the TMS is equally effective after a positive acute response, many clinicians and researchers

have questioned the current clinical protocol of waiting for a relapse to start treating with TMS. Succinctly, should we be using TMS to maintain response?

Research using TMS as a maintenance therapy has shown that remission and response have been extended out for longer periods after the acute treatment, however there has been a multitude of parameters, populations, and treatment protocols used which has led to mixed results. These maintenance protocols studies include: as needed (10), use as a rescue (11), regular weekly or monthly intervals (10), and clustered treatments where multiple treatments are given in the same day (12).

More recently, new acute TMS protocols, called theta-burst have been FDA cleared on some TMS machines for treating depression (9). Both the original 10hz stimulation approved by the FDA in 2008, and the newer theta-burst stimulation are excitatory in nature, but little research has been completed to determine if newer theta-burst protocols are as effective and safe in maintenance of the response compared to acute TMS treatment. Further, no work has been completed on how they compare to the clinical standard 10hz during a maintenance course of treatment.

Hence, the main purpose of this study is to use TMS treatment to maintain patients that have responded or remitted from their depressive symptoms from the use of clinical TMS treatment, while off their antidepressant medication. A secondary objective is to see how the safety and effectiveness of this newer treatment protocol (theta-burst) is compared to prior treatment protocols in a maintenance regime, by comparing the theta-burst to traditional 10hz TMS treatment protocols. An additional tertiary purpose is to see if maintenance therapy treatment performed by a certified TMS technician can be performed without the need of TMS Attending supervision. Given the relative safety of TMS, that TMS technicians are CPR certified, and highly experienced in understanding the safety of TMS, this particular objective would help to show the feasibility and possible economic benefit to patient and provider of not needing Attending supervision for TMS maintenance treatment.

II. Drugs/Biologics/Devices

The device used in this study is a Magventure/MagVita Transcranial Magnetic Stimulation device. It is a FDA approved for treating Major Depressive Disorder in an acute treatment protocol. The normal acute clinical treatment protocol consists of 36 treatments given over 6 weeks with a 3 week taper (totaling 9 weeks). This study will be looking at a maintenance protocol and treating monthly, so there will be much less treatments comparatively. There is no IDE required for this study since it is a FDA approved device and we will use FDA cleared treatment protocols. More specific inclusion criteria are listed in the inclusion/exclusion section of the protocol.

TMS is an electromagnet that uses a small precise, but powerful magnetic pulse delivered to the head corresponding to an area over the brain thought to have some role in the depressive symptoms associated with MDD. This study will use the exact same protocols used in the acute treatment setting, except that treatments will be given monthly not daily (see methods section for reference).

There are currently 3 FDA cleared treatment protocols for acute clinical treatment associated with this device. They consist of a 37 minute treatment, a 20min treatment, and a

3 minute treatment. The 37 and 20 min treatment have similar treatment protocols and total 3000 stimulations for each treatment. Both of these protocols consist of a 10Hz stimulation for 4 secs with either 27 or 11 sec intertrain break with no stimulation respectively. The 3 minute protocol is different than the other two protocols and consists of 600 stimulations per treatment. Its parameters consist of a 50Hz triplet burst stimulation for 2 seconds with a 8 second intertrain break with no stimulation.

Dosage (or % of machine output) is determined by Motor Threshold which is described in the methods section of this protocol.

This device will be used in this study because it is the current device used to treat patients for acute MDD in the UMHC Neuromodulation clinic, and the Neuromodulation clinic is where the subjects for the study will be recruited from.

This study is open-label with no sham group used as a comparative group. However, we will use a study arm that *does not* use a TMS treatment for maintenance and follow them for similar time frame as other study TMS treatment arms noting durability/length of response measures compared to other study treatment groups.

III. Recruitment Process

Subjects will be recruited from the UMHC Neuromodulation clinic. All subjects will already have completed an acute TMS treatment regime in the clinic. This study will be looking at treating in the maintenance phase only, meaning they must previously have completed the acute clinical protocol (36 treatments). Subjects will only come from the UMHC clinic, and must have responded or remitted from their depressive symptoms due to the TMS acute treatment. No participants will be allowed into the study who were acutely treated outside the UMHC Neuromodulation clinic.

As patients come close to the end of their acute clinical TMS treatment, they will be screened to see if their depressive scores have shown a clinically significant improvement, or if their symptoms have remitted (we already collect these scores clinically). If their clinical scores show this inclusion criteria then they will be approached by study staff either through face to face or by letter in mail, letting them know we have a study looking at the efficacy of using TMS treatment to maintain their improvement they have attained in their clinical course of TMS treatment.

If a potential subject is interested in learning more about the study a copy of the consent will be given or sent to them in the mail for them to review, and a consent appointment will be setup to meet with the study staff.

IV. Consent Process

When a potential subject is identified and after a copy of the consent is given to the potential subject for review, a consent appointment will be setup. At the appointment an approved study team member will go over the privacy practices, HIPAA, and consent thoroughly, allowing the potential subject to ask questions and stressing that the signing of the consent is not a contract only a process, and that they can discontinue the study at

any time for any reason. Then if the subject is interested in starting the study the approved team member will have the subject sign and date the HIPAA and consent. Then a copy of each signed document will be given to the subject. A baseline visit will then be setup, or if time allows a baseline visit commence immediately following the signing of consent.

V. Inclusion/Exclusion Criteria

Inclusion Criteria:

[figure not shown]
- Must have recently (within 4 weeks) completed an acute TMS course (full 36 treatments) at the UMHC Neuromodulation clinic
- Must have clinically responded to the acute TMS treatment course ($\geq 50\%$ improvement according to the clinical depressive scale used - usually the PHQ-9)
- Must be able sign consent
- Must have a current address and phone number
- Must have current mental health care provider, either psychiatrist or general practitioner who they see for mental health symptom management
- Must be able to taper off antidepressant medication within 2 months of signing consent of study (treatment group only)

Exclusion Criteria:

- Subject that has not completed a full acute treatment course, including taper
- Subjects that have changed anything that may not make them safe for TMS, which are (all changes will be reviewed by study MD, and will not necessarily be excluded possibly depending on severity):
 - o Any new metal near head
 - o Any new medical devices that cannot be removed
 - o Any new pregnancies (verbally confirmed)
 - o Seizures that occurred post-acute TMS treatment
 - o Any uncontrolled cardiovascular disease
 - o Any new head trauma
 - o Any new illness causing injury to brain
 - o Any new medications which cannot be altered or lowered that may be contraindicated for TMS treatment
 - o Any drug or alcohol use deemed by the study doctor as unsafe for TMS treatment
- Subjects unwilling to sign consent or follow study procedures
- Subjects with known extended travel plans which may affect study procedures and scheduled TMS treatment

VI. Number of Subjects

For this study we are looking to enroll 120 subjects broken down between 2 different treatment arms in the following way:

The number of subjects we expect to enroll is based on our current UMHC Neuromodulation clinic patient flow. The average patient clinic flow is 100 per year and using these numbers the study should be able to complete within 1-2 years. We expect that at least 20% of our expected enrolled may drop out of study for varies reasons (moved, loss of interest, unexpected reasons) hence the total expected completed being 100. 60 subjects in each arm will allow for a balanced study.

VII. Study Procedures/ Design/Treatment Plan

This is an open-label non-blinded study, for patients that have already completed an acute TMS course of therapy and have responded or remitted from their depressive symptoms according to their routine care clinical assessments (PHQ-9, or QIDS). There is no sham treatment in this study, but we will be using a study arm that does not receive TMS treatment in order to compare to an active TMS study arm.

All subjects will complete 3 non-treatment visits (consent, baseline, end of study visit) and if a subject is in the treatment arm and additional 60 visits (over the course of year). Additionally, a subject that is in the treatment arm will completed a PHQ-9, and IDS at baseline visit, and the beginning and end of each monthly treatment block. If a subject is in the non-treatment arm they will complete 15 total visits consisting of a consent, baseline, 12 assessment visits (for PHQ-9 & IDS testing) and an end treatment visit. For these individuals, a PHQ-9 and IDS will be completed at the baseline visit and at each monthly assessment visit.

[figure not shown]
Subjects in the active TMS treatment arm will be tapered off their antidepressant medication as soon as they have signed consent according to the study doctor's direction. Subjects in the TMS active arm will remain antidepressant medication free for the duration of the study. If these subjects deteriorate during course of the study they will be removed from the study and normal clinical care will resume. They will complete a PHQ-9 and QIDS at this time. Their data will be used in the final analysis of study. Deterioration or relapse will be determined by the study doctor clinical judgement.

For subjects in the active TMS treatment arms, a dosing procedure (Motor Threshold) will need to be performed by any person the study PI delegates this authority to, each month immediately before the first treatment of each monthly treatment block. The Motor Threshold (MT) is used to determine the % TMS machine output or dosage, needed to treat. The procedure consists of the TMS certified operator placing the TMS machine treatment coil on the patient's head, corresponding to an area over the patients left Motor Cortex of his/her brain. Then the TMS machine intensity is turned up or down and the coil is moved around on patient's head to determined how much energy is need to elicit a muscle twitch in the right abductor pollicis brevis muscle (APB). Then a computer algorithm helps determine the correct intensity that should be used for the next 5 treatments. An additional computer algorithm uses head measurements of circumference, Nasion to Inion, and Tragus to Tragus, to determine where the TMS treatment coil will be located to treat over the Dorsolateral Prefrontal Cortex (DLPFC). This procedure must be completed each month prior to the monthly treatment block.

If a patient drops out of the study for any reason their data up to that point will be retained and used, this will be discussed with the potential patient during the consent process, and described in the consent itself.

The last treatment visit when a patient completes the treatment portion of the study or has finished their last monthly assessment visit if they are not in an active treatment arm, will be an end study visit (this could be the last treatment/assessment visit if time allows). At this visit the TMS MD will discuss end of study and possible future clinical care that maybe necessary for subject when they switch back over to clinical realm and are no longer part of the study.

Study procedure plan is below:

Study visit completion for TMS active arms form is below, subjects that are in non-active arm will not have the TMS treatment visits, but will do the monthly assessment visits:

Visit	Consent	Hipaa	Inclusion/Exclusion	TASS	PHQ-9*	QIDS*	AE **
Consent	x	x					
Baseline			x	x	x	x	
Trt 1-5 (1 Month)					x	x	
Trt 6-10 (2 Month)					x	x	
Trt 11-15 (3 Month)					x	x	
Trt 16-20 (4 Month)					x	x	
Trt 21-25 (5 Month)					x	x	
Trt 26-30 (6 Month)					x	x	
Trt 31-35 (7 Month)					x	x	
Trt 36-40 (8 Month)					x	x	
Trt 41-45 (9 Month)					x	x	
Trt 46-50 (10 Month)					x	x	
Trt 51-55 (11 Month)					x	x	
Trt 56-60 (12 Month)					x	x	

* Completed before and after each monthly TMS treatment block

** Adverse Event form to be filled out as needed

VIII. Potential Risks/Adverse Events

The machine and treatment protocols are the same used in the clinical setting, therefore the risks are the same. The most common side effect/ risk is headache, superficial pain under treatment site, dental pain, eye pain, or facial muscle twitching. These seem to well tolerated, and can occur during or after treatment. These can be treated with over-the-counter pain medication (Tylenol, Ibuprophen).

Another rare but serious risk is seizure. Seizures are very rare and are thought to occur about 1 in 30,000 treatments. Subjects will have already gone through safety screens in order to get TMS treatment clinically, but nevertheless, another Transcranial Adult Safety Screen (TASS) will be done prior to starting treatment phase of study. Study staff are trained in seizure occurrence during TMS and are also CPR certified.

The study doctor will determine if patient participation should start or continue from these or any other subject problems that may occur, such as failure of TASS question throughout the study.

If an adverse event, UP, or deviation occur study staff will fill out a study adverse event form, the AE event log, and will notify the MU IRB if required within 5 days of awareness of the event.

IX. Anticipated Benefits

It is not known whether TMS used in a monthly maintenance protocol will be beneficial in helping to extend out the subject's acute response or remission, but it may be a possible benefit. Additionally, this study will help add to the work of clinical and scientific community in this area of interest. This data may also help future patients that have MDD and are trying to maintain their response.

X. Compensation

No compensation will be given for this study.

XI. Costs

There are no costs associated with this study either for the research or to participants. The TMS machine is already part of the Neuromodulation Clinic.

XII. Data Safety Monitoring Plan

No DSMB is required for this study. All adverse events will be reported on the AE study report form, the AE log, and local IRB protocol will dictate what needs to be submitted to MU IRB. Because this is an internal study (no other sites), AEs and UP will immediately be known to study doctor. He will determine if AEs are in the normal range

for TMS treatment, comparing to clinical experience and TMS safety data. If they are found not to be, the he may pause the study to review protocols and procedures.

All study data will be captured on paper then transferred over to an electronic database on a secured approved UM computer. All data will be coded so no patient data will be identifiable. Study Consents and HIPAA that are signed will be stored in locked cabinet behind a locked door. The key linking subject consent and subject codes will not be stored in same place as consents and coded data. All coded data on paper will be placed in subject binder and stored in locked cabinet behind locked door. All study data will be stored for length of time in accordance with UM IRB research data rules.

XIII. Multiple Sites

1. NA

XIV. References/Appendices

- 1 O'Reardon, J. P., Solvason, H. B., Janicak, P. G., Sampson, S., Isenberg, K. E., Nahas, Z., ... & Demitrack, M. A. (2007). Efficacy and safety of transcranial magnetic stimulation in the acute treatment of major depression: a multisite randomized controlled trial. *Biological psychiatry*, 62(11), 1208-1216.
- 2 Carpenter, L. L., Janicak, P. G., Aaronson, S. T., Boyadjis, T., Brock, D. G., Cook, I. A., ... & Demitrack, M. A. (2012). Transcranial magnetic stimulation (TMS) for major depression: a multisite, naturalistic, observational study of acute treatment outcomes in clinical practice. *Depression and anxiety*, 29(7), 587-596.
- 3 Janicak, P. G., Nahas, Z., Lisanby, S. H., Solvason, H. B., Sampson, S. M., McDonald, W. M., ... & O'Reardon, J. P. (2010). Durability of clinical benefit with transcranial magnetic stimulation (TMS) in the treatment of pharmacoresistant major depression: assessment of relapse during a 6-month, multisite, open-label study. *Brain stimulation*, 3(4), 187-199.

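### In the visible text only the TMS arm has antidepressants withdrawn, so the durability comparison measures maintenance TMS plus withdrawal, and a null or adverse result could not be read as TMS failing

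*Protocol*

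**What the plan says.** The medication rule for the active arm is explicit. Section VII: "Subjects in the active TMS treatment arm will be tapered off their antidepressant medication as soon as they have signed consent", and then "Subjects in the TMS active arm will remain antidepressant medication free for the duration of the study". Section I gives the reason: the main purpose is to maintain patients who responded or remitted "from the use of clinical TMS treatment, while off their antidepressant medication".

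The matching entry criterion in section V applies to one arm: "Must be able to taper off antidepressant medication within 2 months of signing consent of study (treatment group only").

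The comparator is defined only by the absence of TMS. Section VII: "we will be using a study arm that does not receive TMS treatment in order to compare to an active TMS study arm". Section II says this arm will be followed for a similar time, "noting durability/length of response measures compared to other study treatment groups". Its monthly contacts are described in section VII as "12 assessment visits (for PHQ-9 & IDS testing"). No readable text says whether these participants continue, stop or change antidepressants.

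Some material is missing from the copy at hand: a figure in section V under the inclusion criteria, the arm breakdown in section VI, and a figure and the procedure plan in section VII. A medication rule for the no-TMS arm could sit in one of them.

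**The concern.** As far as the visible text goes, the two arms differ by protocol in two respects: monthly TMS (yes or no) and antidepressant withdrawal (imposed or not). With two arms, only the joint effect of the two can be estimated. An analysis plan could not separate them, because withdrawal is fixed by arm.

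The protocol nevertheless labels the contrast as TMS against no TMS, and a reader would take the result as the effect of TMS. If stopping antidepressants raises relapse risk and controls stay on theirs, withdrawal works against TMS. A useful maintenance schedule could then look weak, useless or harmful. After up to 60 treatment visits per active participant, a null result could not tell ineffective TMS from effective TMS offset by withdrawal.

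**Working it through.** The protocol states no effect size, power or hazard ratio for this comparison, so there is no figure of its own to reproduce. The check has two parts.

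**1. Rules by arm**

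| | Active TMS arm | No-TMS arm |
|---|---|---|
| Monthly TMS | Yes (VII) | No (II, VII) |
| Must be able to taper | Yes, within 2 months of consent (V) | Not required (V) |
| Antidepressants withdrawn | Yes, from consent (VII) | No rule visible |
| Kept off antidepressants | Yes, throughout (VII) | No rule visible |
| Antidepressant use on the visit schedule | No item (VII) | No item (VII) |

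**2. How much withdrawal could matter (illustration only)**

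Inputs:
- Background risk, section I: "close to 40% of patients will see symptom worsening, and another 10% will have a relapse within 6 months post-acute treatment course". The main anchor is 10% relapse at 6 months. The protocol does not say whether those patients were medicated.
- Withdrawal takes effect from month 2 to month 12. Month 2 is the latest completion of the taper that section V allows; an earlier taper would enlarge the effect.
- Assumed, not from the protocol: hazard ratio for TMS T = 0.5 or 0.7; hazard ratio for withdrawal w = 1.0, 1.5, 2.0 or 2.5; constant hazard; no interaction.

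Control hazard: h = -ln(1 - 0.10)/6 = 0.0176 per month. Control risk at 12 months: 1 - exp(-12h) = 19.0%.

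*Scenario A: all participants medicated at entry, all controls stay medicated.* Active risk = 1 - exp(-h(2T + 10Tw)). For T = 0.5 and w = 2.0 the exponent is 0.0176 × (1 + 10) = 0.193, which gives 17.6%.

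| w | Active, T = 0.5 | Minus control (points) | Active, T = 0.7 | Minus control (points) |
|---|---|---|---|---|
| 1.0 | 10.0% | -9.0 | 13.7% | -5.3 |
| 1.5 | 13.9% | -5.1 | 18.9% | -0.1 |
| 2.0 | 17.6% | -1.4 | 23.7% | +4.7 |
| 2.5 | 21.1% | +2.1 | 28.2% | +9.2 |

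The TMS benefit is exactly cancelled when 2T + 10Tw = 12, that is, at w = 2.2 for T = 0.5 and w = 1.51 for T = 0.7.

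*Scenario B: half medicated at entry, medicated controls stay on.* Active risk is the mean of the scenario A value and 1 - exp(-12hT). Over w = 1.0 to 2.5 it runs from 10.0% to 15.6% (T = 0.5) and from 13.7% to 21.0% (T = 0.7), against 19.0% in controls.

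*Scenario C: all medicated at entry, half of the controls also stop on the same timing.* Control risk is the mean of 19.0% and 1 - exp(-h(2 + 10w)), which is 19.0, 22.4, 25.5 and 28.4%. Active minus control is -9.0, -8.5, -8.0 and -7.3 points (T = 0.5) and -5.3, -3.5, -1.8 and -0.1 points (T = 0.7).

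*Scenario D: half medicated at entry, half of the medicated controls stop.* The difference runs from -9.0 to -8.1 points (T = 0.5) and from -5.3 to -2.7 points (T = 0.7).

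*Upper anchor.* Adding worsening and relapse gives 40% + 10% = 50% at 6 months, so 75.0% in controls at 12 months. With the scenario A assumptions, active risk is 50.0, 62.5, 71.9 and 79.0% (T = 0.5) and 62.1, 74.7, 83.1 and 88.7% (T = 0.7).

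**The case against.** The strongest defence is that the asymmetry is deliberate and declared. Section I sets out to maintain responders on TMS without antidepressants, and sections V and VII carry that out openly. The contrast can be read as one of strategies, TMS replacing drugs against no TMS, and no visible text states a superiority hypothesis for TMS alone. This stands as a reason not to call the design wrong. It does not remove the point: the strategy reading itself concedes that the contrast is TMS plus withdrawal, and sections II and VII do not describe it so.

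Four stronger readings are tempting, and the protocol does not support them:

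- *That no between-arm result could inform about TMS.* If withdrawal is harmful and controls stay medicated, the bias runs against TMS. A difference in its favour would then be conservative with respect to medication. Only null or adverse results lose their meaning.
- *That controls stay on antidepressants.* The visible text says only that they need not taper. Participants already off antidepressants at consent are unaffected.
- *That the arms differ by selection, because only one must be able to taper and no randomisation is mentioned.* This leans on silence in a text whose arm breakdown and figures are missing, and carries no weight here.
- *That the ability-to-taper criterion should therefore bind both arms.* This would exclude controls for something they are never asked to do, and could cost recruitment. About 100 clinic patients a year (section VI) for two years, with roughly 2/3 benefiting (section I), gives about 133 candidates for 120 places, if that benefit approximates the response criterion. If 20% could not taper (assumed), about 107 would remain.

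It is also fair to say that medication use is often captured on case report forms without appearing in a visit table. The recording request may therefore only make explicit what is already intended.

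**Conclusion.** The point holds in a limited form. As visible, the durability comparison estimates maintenance TMS with antidepressant withdrawal against no TMS without protocol withdrawal, although it is presented as TMS against no TMS. This is conditional on no control-arm medication rule in the missing material.

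The size is unknown, since no text supports a particular withdrawal hazard ratio. Across the illustrated range the effect runs from nothing to reversal of a true benefit. It is largest if everyone is medicated at entry and all controls stay so, and much smaller if many are unmedicated at entry or controls stop too. The direction, understating TMS, rests on two assumptions: that withdrawal raises relapse risk, and that controls largely stay medicated.

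The main purpose in section I survives, because the active arm alone can describe how many patients stay well without antidepressants. The matter is worth correcting because it decides what a null or adverse comparison may be said to show.

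**What to change.** (a) State the comparison and its permitted conclusion as maintenance TMS with antidepressants withdrawn, versus no TMS with antidepressants not withdrawn by protocol. Say that a null or adverse result supports no claim about TMS alone.

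(b) Record antidepressant use in both arms at consent, before any taper, and at each scheduled monthly visit. Report durability alongside it by arm.

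The cost is a change of wording, a narrower claim, and one extra data item at consent and at the 12 monthly time points already planned. No new visits or arms are needed, and no control has to stop treatment. Extending the ability-to-taper criterion to controls, or using the same antidepressant rule in both arms, is a design decision for the investigators and not part of this fix. If a control-arm medication rule already exists in the missing material, the wording in (a) should follow it.

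### The active-arm antidepressant taper is set to start at consent, although eligibility, TASS and the first study depression scores belong to a baseline visit that may come later

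*Protocol*

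**What the plan says.** **Start of the taper.** Section VII states that active-arm subjects "will be tapered off their antidepressant medication as soon as they have signed consent according to the study doctor's direction". Section V sets the time allowed: "Must be able to taper off antidepressant medication within 2 months of signing consent of study (treatment group only". That window runs from consent and applies to the active arm alone.

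**Baseline visit.** Section IV, on what follows signature: "A baseline visit will then be setup, or if time allows a baseline visit commence immediately following the signing of consent". Section VII counts consent and baseline as separate non-treatment visits.

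**What is done when.** In the Section VII visit table, the consent row marks only consent and HIPAA. The baseline row marks inclusion/exclusion, TASS, PHQ-9 and QIDS.

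**Provisions that bear on the gap.**
- Section III: response is screened from routine clinic scores before a patient is approached ("we already collect these scores clinically").
- Section V: for new safety-relevant events since the acute course, "all changes will be reviewed by study MD, and will not necessarily be excluded possibly depending on severity".
- Section VIII: "another Transcranial Adult Safety Screen (TASS) will be done prior to starting treatment phase of study", and "The study doctor will determine if patient participation should start or continue".

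**The concern.** The taper is the one study step in the active arm that takes away something the patient already has. As written, it is triggered by a signature, while the formal decision on whether the patient belongs in the study waits for a visit that may fall on another day. Two of the inclusion criteria due at that visit bear directly on stopping medication: being able to taper within two months, and having a current mental health provider.

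Two things are at stake. First, a subject found ineligible at a later baseline (for example because of a new pregnancy, or a seizure since the acute course) may already have begun withdrawal, and would not get the maintenance TMS that the withdrawal was meant to accompany. Second, the first study PHQ-9 and QIDS may be taken partway through a taper in the active arm. The comparator has no protocol taper, so the two arms' baselines would not describe the same state.

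**Working it through.** The point concerns the order of procedures. The protocol gives no figure to reproduce, so the provisions are set side by side first.

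**Order permitted by the text, active arm**
1. Clinic scores show response (Section III).
2. Consent and HIPAA are signed (Section IV; consent row of the table).
3. The taper starts (Section VII).
4. Baseline: inclusion/exclusion, TASS, PHQ-9, QIDS (baseline row), on the same day or later (Section IV).
5. First TMS treatment, which must follow TASS (Section VIII).

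No provision shown makes step 3 wait for step 4. The TASS rule in Section VIII holds back step 5 only. Response is settled at step 1 and is not part of the gap.

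**How long the gap can be.** Section IV gives no interval, but Section V requires the acute course to have been completed within 4 weeks. If that criterion is checked at baseline, as the table schedules, and consent is signed *t* weeks after the course ends, then

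gap ≤ 4 − *t* weeks.

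A 4-week gap therefore needs consent on the day the course ends. The cap is approximate, because Section V does not name the visit to which the 4 weeks are measured.

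**How far into the taper baseline could fall.** One month = 365.25 / 12 / 7 = 4.35 weeks, so the window is 2 × 4.35 = 8.70 weeks. The gaps are assumed, and the taper is taken to use the whole window. Shares are of elapsed time, not of dose.

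| Assumed gap (weeks) | Share elapsed = gap / 8.70 | Weeks left if taper waits and window stays at consent = 8.70 − gap |
|---|---|---|
| 0 | 0% | 8.7 |
| 1 | 11.5% | 7.7 |
| 2 | 23% | 6.7 |
| 4 | 46% | 4.7 |

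A shorter taper would be further along at the same gap.

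**How many subjects.** Section VI plans 60 per arm, so at most 60 are exposed. The share with a later baseline and the share then excluded are not in the protocol. For illustration only:
- Later baseline in 10%, 25% or 50% (assumed): 60 × 0.10 = 6; 60 × 0.25 = 15; 60 × 0.50 = 30.
- Of those, 2% to 5% excluded at baseline (assumed): from 6 × 0.02 = 0.12 to 30 × 0.05 = 1.5 subjects.

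These counts rest wholly on the assumed rates and show only the likely order of size.

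**The case against.** The best reply is that the taper is not automatic. It follows the study doctor's direction. Section IV lets any approved team member take consent, so starting the taper needs a separate act by the doctor. The same doctor decides whether participation starts, and the study MD reviews each new safety event and need not exclude. Subjects have just finished treatment at the same clinic and passed its screens. Anyone excluded should have a mental health provider to return to. A figure is missing from the text just before the taper sentence and may show the intended order.

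Much of this stands and keeps the point small. It does not remove it. The doctor could delay the taper, but the sentence that sets its timing points to immediate start. Earlier clinic screens cannot fully cover events new since the acute course. The provider criterion is itself due for checking at baseline. If the missing figure shows the right order, the sentence would still need to match it.

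Three stronger readings may tempt a reader, and the protocol does not support them:
- *That patients are withdrawn before checks which protect them from withdrawal.* TASS and most of the listed exclusions concern the safety of TMS, and for TMS the order is correct. The risk is a needless start of withdrawal in someone later excluded.
- *That the gap is unlimited.* The 4-week criterion roughly caps it if checked at baseline.
- *That the arm comparison is biased by a known amount.* No change-from-baseline endpoint is stated, and clinic scores from before consent give a partial reference on at least one scale.

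**Conclusion.** The point holds as a minor one. The protocol's wording allows the active-arm taper to begin before eligibility, TASS and baseline scores are complete whenever baseline is not on the day of consent. The exposed group is at most 60 subjects. The number who would begin withdrawal and then be excluded cannot be derived from the document and is likely small. The delay is probably no more than about 4 weeks, on the assumption that the 4-week criterion is applied at baseline. The effect on baseline comparability is real in kind, but its size cannot be stated. With a same-day baseline the problem disappears if the scores and checks precede the first dose reduction. The point is worth raising because the rule as stated gives a worse order than is needed and can be corrected at almost no cost.

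**What to change.** Reword the taper sentence in Section VII so that the active-arm taper starts only after inclusion/exclusion, TASS and baseline PHQ-9 and QIDS are completed, on the day of consent where possible. The pace stays with the study doctor.

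The two-month window in Section V may stay counted from consent. Moving it to baseline is not needed and, done alone, would loosen the only firm off-drug deadline. If it is moved, also set a maximum interval between consent and baseline.

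The cost is one reworded sentence. Subjects with a same-day baseline lose nothing. For the others the taper starts later by the gap and, if the window stays at consent, has less time to finish: 7.7, 6.7 or 4.7 weeks instead of 8.7 for assumed gaps of 1, 2 or 4 weeks.
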